12.1 Stopping the Study Based on Interim Safety Data

The IMR will receive periodic safety reports of all AEs and SAEs. This study can be temporarily suspended or stopped to evaluate any negative safety trends.

12.2 Clinical Study Termination/Withdrawal

Subjects may be terminated or withdrawn from the study for the following reasons:

- Voluntary withdrawal of consent: meaning that a subject voluntarily chooses not to participate further in the study. All data collected up to the withdrawal of consent will be maintained in the study database. Withdrawn subjects will not have any additional follow-up and will not be replaced.
- Lost to follow-up: a subject will be considered lost-to-follow-up when contact is not achieved at the last required follow-up visit window. At a minimum, the effort to obtain follow-up information will include three (3) attempts to make contact via telephone or e-mail and if unsuccessful, then a letter from the Investigator sent via courier or other traceable method will be sent to the subject's last known address. These efforts to obtain follow-up will be recorded in the subject's study files.
- Withdrawn by Investigator: Subjects may be withdrawn at the Investigator's discretion if within their best interest. A subject's participation in the clinical study will be terminated if the Investigator believes that this is in the subject's best medical interest or if the subject no longer complies with the clinical study requirements.

The sponsor may temporarily suspend or prematurely terminate the study at any time for the following reasons:

• Suspicion of risk to subjects

- If no positive IRB decision is obtained or if the judgement of the IRB is revoked
- If the applicable regulatory body has made an irrevocable objection
- If it transpires that continuation of study cannot serve any scientific purpose, and this is confirmed by the IRB
- Business reasons

The Sponsor will document reasons for study suspension or premature termination and notify the PIs. The Sponsor will ensure that the IRB and regulatory authorities are notified in a timely manner.

The Sponsor will continue to provide resources to fulfill the obligations from the study protocol and existing agreements for following up the subjects enrolled in the study.

The Principal Investigators will promptly inform the enrolled subjects at his/her site, if appropriate.

If the Sponsor temporarily suspends the study and wishes to resume it, the Sponsor will inform the PIs, IRB, and (if appropriate) regulatory authorities. The Sponsor will provide a rationale for resuming the study. IRB must provide written approval before the study is resumed.

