6.7.6 Discharge (or 7 days, whichever occurs first)

The following information will be collected during discharge (within 1 day prior to discharge or at day 7, whichever occurs first):

- 1. Vital Signs
- 2. Laboratory assessments
- 3. 12 lead ECG
- 4. Killip Classification
- 5. CCS Classification
- 6. Cardiac concomitant medications
- 7. Events of interest/Serious Adverse Events

6.7.7 **30 Day Visit (± 7 days)**

The 30-day follow up visit may be conducted either over the phone or in person. Records within the study visit window from an outside Institution may be used to complete the visit. It is recommended that at a minimum, study patients are contacted via phone by the study site team. The following information will be collected during the 30-day follow up visit:

- 1. Subject status
- 2. NYHA Classification
- 3. Killip Classification (if visit completed in person)
- 4. CCS Classification
- 5. Cardiac concomitant medications
- 6. Events of interest/Serious Adverse Events

6.7.8 180 Day Visit (± 30 days)

The 180-day follow up may be completed over the phone or in person. Records within the study visit window from an outside Institution may be used to complete the visit. It is recommended that at a minimum, study patients are contacted via phone by the study site team. The following information will be collected during the 180-day follow up visit:

- 1. Subject Status
- 2. Vital Signs
- 3. NYHA Classification
- 4. Killip Classification (if visit is completed in person)
- 5. CCS Classification
- 6. 12 Lead ECG
- 7. Echocardiogram (if completed as SOC assessment can occur anytime between the 30 day and 180 day follow up windows)
- 8. Cardiac concomitant medications
- 9. Events of interest/Serious Adverse Events

Table 2: Schedule of Assessments

ACTIVITY	Baseline/Pre- Procedure	Procedure (Day 0)	Post-Procedure	Discharge or 7-Days (whichever occurs first)	30 days ± 7 days (Phone Call or In Person)	180 days ± 30 days (Phone Call or In Person)
Written Informed Consent	X1					
Confirm Eligibility Criteria	х	X ²				
Demographics	х					
Medical History	Х					
Vital Signs	X		X	Х		X
Laboratory Assessments	х		x	Х		
Pregnancy Test	X ³					
NYHA Classification	x				X	x
Killip Classification	x			x	Xº	Xº
CCS Classification	х			х	X	х
12 Lead ECG	х		X	Х		Х
Coronary Cineangiography		X4,5				
Echocardiogram ⁶	x		X		2	ζ ⁷
TIMI Flow Grade Score		X ⁵				
TIMI Thrombus Grade		X ⁵				
Myocardial Blush Grade		X5				
Target Lesion Characteristics		х				
Procedure		X				

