7.6.1 Adverse Events

Adverse events (AE) must be recorded by the Investigator on the CRFs and must be monitored during the study. Primary and secondary safety endpoint events, all device or procedure related events, all Serious Adverse Events (SAE), and all Unanticipated Adverse Device Effects (UADE) will be collected starting at Procedure (Day 0) through final follow-up visit. Minimum requirements of data to be recorded are: event term, event start date, seriousness, action taken, outcome and device-relatedness.

In order to ensure prompt reporting of AEs, all reportable AEs (as well as all related study data) are required to be entered into the EDC in a timely manner. Any suspected UADEs should be reported immediately by calling the Sponsor. All device related SAEs should be reported in the EDC within 72 hours of the site staff first being made aware of the occurrence of the SAE. If the EDC is unavailable, an email can be sent to Penumbra.

The Investigator must report adverse events to the IRB according to local requirements. The Investigator is responsible for adhering to reporting time frames and complying with local and federal requirements. In addition, the Investigator will report to the Sponsor and IRB any device deficiencies that could have led to a SAE, if required by federal regulations or by local authorities.

For the purpose of reporting within this protocol, pre-existing conditions or planned procedures for pre-existing conditions are not reportable as AEs unless there is worsening of the condition with an increase in severity or frequency during the course of the study.

All deaths will be reported regardless of causality. When reporting a death, the primary condition or diagnosis that contributed to the fatal outcome should be reported as a SAE, with an outcome of death. Only a single cause of death should be reported in EDC. If the cause of death is unknown, report "unknown cause of death" as a SAE.

Detailed form and narrative reports will be composed for primary and secondary safety endpoints (at a minimum).

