10.4 Missing Data and Imputation Methods

Every effort will be made to keep all missing data, particularly the 30-day outcomes, to a minimum. Some data may be missing, mainly due to lost-to-follow-up (LTFU) subjects. The primary analysis will be data as observed. Sensitivity analysis will be performed.

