Completed subjects are all subjects who were enrolled and completed the study followup or were known to have died prior to the final follow-up time point. The completed subject metric will be provided for 180-day follow-up.

• Early Termination:

Early termination subjects are all subjects who were enrolled but did not complete follow-up and were not known to have died. The early termination subject metric will be provided for 180-day follow-up.

6 Definition of Analysis Populations

• Intent to Treat Sample:

As the primary analysis, all performance and safety outcome measures will be analyzed under the Intent-To-Treat (ITT) principle. Under this principle, the ITT sample includes all subjects who are enrolled. This population is the primary analysis population.

• Per-Protocol Sample:

In addition to the defined ITT analysis sample, a per-protocol (PP) sample is defined as a subset of the ITT sample. The per-protocol sample will include ITT population who do not have significant protocol deviations (e.g. eligibility violation) according to the CHEETAH study protocol version at the time of database lock.

7 Statistical Analysis

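### Protocol Section 12.2 lets a subject be declared lost with no check on vital status, and the SAP plans no missing-data sensitivity analysis for 180-day mortality

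*Combined protocol and SAP*

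**What the plan says.** - **Tracing (protocol 12.2).** The required minimum is "three (3) attempts to make contact via telephone or e-mail and if unsuccessful, then a letter from the Investigator sent via courier" or by another traceable method. The letter "will be sent to the subject's last known address". The section mentions no alternate contact, treating physician, hospital record or death-record search.
- **Timing (protocol 12.2).** "a subject will be considered lost-to-follow-up when contact is not achieved at the last required follow-up visit window". Under protocol 6.2 that window is 180 ± 30 days.
- **Other sources (protocol 6.7.7 and 6.7.8).** "Records within the study visit window from an outside Institution may be used to complete the visit". This is optional. Both visits may be done by telephone.
- **Deaths (protocol 7.6.1 and 16.2).** "All deaths will be reported regardless of causality". Deaths of unknown cause count as cardiovascular.
- **Classification (protocol 10.5.5, SAP 5).** "Early termination subjects are all subjects who were enrolled but did not complete follow-up and were not known to have died".
- **Analysis.** Under protocol 10.4 and SAP 10, "The primary analysis will be data as observed". SAP 4 summarises the observed data at each visit. SAP 7.2 reports 180-day all-cause and cardiovascular mortality as proportions with 95% confidence intervals and by Kaplan-Meier. SAP 10 defines three sensitivity analyses (exclusion, worst case, best case), all for the 30-day primary endpoint.

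**The concern.** The rules on deaths work only once the site knows of the death. A subject who dies after discharge, away from the treating hospital, may simply not answer. The site can then meet the whole of the 12.2 minimum, close the case as lost, and never have been required to ask whether the subject is alive. In the analysis that subject is an early termination.

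If death is the reason for the silence, the censoring is informative. A proportion based on observed subjects omits the death, and a Kaplan-Meier estimate censors the subject at last contact as though the later risk were that of everyone else. Both errors favour the device. All-cause and cardiovascular mortality within 180 days are named secondary safety endpoints of a study whose purpose is safety, and no planned analysis would show how far the estimates depend on the subjects with unknown status.

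**Working it through.** **1. The plan's own figures.** SAP 2 gives 360 subjects, a 6.1% event rate (22/360), one-sided alpha 0.025 and 99% power; the success limit is 16% (SAP 7.1). An exact binomial test against 16% succeeds with at most 43 events in 360 (exact alpha 0.0185). Power at 22/360 is 99.999%, consistent with the stated 99%. Inflation for attrition: 360 / (1 − 0.10) = 400, as stated. Tracing does not affect these figures.

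**2. The primary endpoint.** The upper limits below are exact (Clopper-Pearson); the plan does not name an interval method. Take 22 events in 360 observed subjects and 40 missing.

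| Missing subjects counted as events | Events / N | Rate | Upper 95% limit | Below 16%? |
|---|---|---|---|---|
| none; missing excluded | 22/360 | 6.1% | 9.1% | yes |
| 27 of 40 | 49/400 | 12.25% | 15.9% | yes |
| 28 of 40 | 50/400 | 12.5% | 16.1% | no |
| 40 of 40 (SAP worst case) | 62/400 | 15.5% | 19.4% | no |

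The conclusion changes only if at least 28 of the 40 (70%) had an event, and the worst-case analysis that would expose such sensitivity is already planned.

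**3. 180-day mortality.** The documents give no planning rate for mortality and no expected death rate among lost subjects, so these inputs are assumptions:

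- mortality among followed subjects: 4%;
- number lost: 40 of 400 (the plan's attrition ceiling of 10%) or 20 of 400 (5%);
- share *d* of the lost who have died: 4%, 10% or 20%.

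True rate = [(400 − lost) × 0.04 + lost × *d*] / 400. If lost subjects leave the denominator, the reported rate is 4.0% and the relative understatement is 1 − 0.04 / true rate.

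| Lost | *d* | Deaths (followed + lost) | True rate | Understatement |
|---|---|---|---|---|
| 40 | 4% | 14.4 + 1.6 = 16.0 | 4.0% | 0% |
| 40 | 10% | 14.4 + 4.0 = 18.4 | 4.6% | 13% |
| 40 | 20% | 14.4 + 8.0 = 22.4 | 5.6% | 29% |
| 20 | 4% | 15.2 + 0.8 = 16.0 | 4.0% | 0% |
| 20 | 10% | 15.2 + 2.0 = 17.2 | 4.3% | 7% |
| 20 | 20% | 15.2 + 4.0 = 19.2 | 4.8% | 17% |

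The SAP does not state the denominator for the 180-day proportions, and its ITT sample is all enrolled subjects. If all 400 were used with 40 lost, the reported rate would be 14.4/400 = 3.6%. The understatement would then be 1 − 3.6/4.6 = 22% at *d* = 10% and 1 − 3.6/5.6 = 36% at *d* = 20%. Even at *d* = 4% it would be 1 − 3.6/4.0 = 10%.

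**The case against.** The strongest reply is that 12.2 sets a floor and that deaths come to light in other ways. Much of this stands.

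- The tracing steps are stated as a minimum. A call or letter to the home may reach family who report the death, some subjects have a legally authorised representative, and in-hospital deaths are known to the site. A reader might infer that the steps can never detect a death, or that mortality will be understated. The documents support neither; this is a risk. But the minimum is all a site must do to close a case, and hearing of a death by chance is not ascertainment.
- A reader might also infer that the visit-window limit on outside records bars, for example, a hospital record of a death on day 80. It does not. That sentence governs completing a visit. Deaths are reportable through the final follow-up visit, and protocol 7.6.1 sets no date limit on the source. What is missing is any duty to look for such a record.
- Other text helps: subject status is collected at 30 and 180 days, a missed visit prompts contact to reschedule (12.3), monitors resolve missing data (8.4.3), and discontinuations are tabulated by reason (SAP 10). None of these requires vital status to be established for a subject who cannot be reached.
- It is tempting to extend the point to the 30-day primary result. Loss is declared only at the last visit window, and the primary endpoint has its own worst-case analysis, so that reading is not supported.
- The 180-day mortality endpoints carry no test or threshold. With 14 deaths in 360, the exact 95% interval is 2.1% to 6.4%, which contains the true rates of 4.6% and 5.6% above. No planned decision turns on the bias. A systematic error in a safety estimate is still worth removing, because the interval does not account for it.
- The 10% attrition allowance does not separate loss from withdrawal of consent, and withdrawn subjects have no further follow-up. Forty lost subjects is therefore a ceiling.

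**Conclusion.** The point holds as a gap in ascertainment and in sensitivity analysis for 180-day all-cause and cardiovascular mortality. Section 12.2 requires no vital-status step before loss is declared, an unrecognised death becomes an early termination, and nothing in the SAP would show the effect on those two endpoints.

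Any bias from unrecognised deaths is downward. Its size rests on assumptions that the documents cannot settle. With 4% mortality among followed subjects, 5% to 10% lost, and lost subjects outside the denominator, it runs from zero (equal death rates) to about 7% to 29% relative understatement (10% to 20% of the lost have died). With few lost subjects it would be small. The primary conclusion is robust at the planned event rate. This is an inexpensive improvement that should be made; it is not a flaw in the main result.

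**What to change.** **Protocol 12.2.** Before a subject is declared lost at the last required visit window, require a documented vital-status check using:

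- an alternate contact recorded at enrolment;
- treating-hospital or physician records of any date;
- a public death-record search where permitted.

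Subjects who withdrew consent are not included. Record the date of death or the date last confirmed alive.

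**SAP 7.2 and 10.** Use that date for censoring in the mortality analyses, state the denominator for the 180-day proportions, report the number with unknown vital status, and extend the worst-case and best-case analyses to 180-day all-cause and cardiovascular mortality.

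**Cost.** A contact field with matching consent wording, a short search for the few subjects who cannot be reached, and two further sensitivity tables. No visits are added. Reported mortality may come out slightly higher.

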12.3 Missing Visits

Every effort should be made to bring subject in to scheduled follow-up visits, within the visit window specified in the protocol. Any study subject who does not attend a scheduled follow-up visit should be contacted by site personnel to reschedule. If the missed visit was due to an adverse event, an AE CRF must be completed and any reporting requirements met.

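### Protocol 12.2 ends participation for non-compliance and makes no provision for collecting outcomes afterwards from subjects who have not withdrawn consent

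*Combined protocol and SAP*

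**What the plan says.** Protocol 12.2 lists three ways a subject may leave the study.

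- **Voluntary withdrawal of consent.** Data up to that point are kept: "All data collected up to the withdrawal of consent will be maintained in the study database". The bullet then adds: "Withdrawn subjects will not have any additional follow-up and will not be replaced".
- **Lost to follow-up.** This status is assigned only at the last required visit window, after at least three phone or e-mail attempts and a traceable letter.
- **Withdrawn by Investigator.** The bullet opens permissively: "Subjects may be withdrawn at the Investigator's discretion if within their best interest". Its next sentence is mandatory: "A subject's participation in the clinical study will be terminated if the Investigator believes" this to be in the subject's best medical interest, or "if the subject no longer complies with the clinical study requirements".

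Other sections bear on the same subjects.

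- Protocol 6.7.7 and 6.7.8 allow the 30- and 180-day visits by phone or in person, and add: "Records within the study visit window from an outside Institution may be used to complete the visit".
- Protocol 12.3 says: "Any study subject who does not attend a scheduled follow-up visit should be contacted by site personnel to reschedule". It also requires an adverse event form if an adverse event caused the missed visit.
- Protocol 10.4 undertakes: "Every effort will be made to keep all missing data, particularly the 30-day outcomes, to a minimum".
- Protocol 10.4 and SAP section 10 base the primary analysis on observed data. SAP section 10 adds sensitivity analyses of the 30-day primary endpoint that exclude subjects with a missing outcome, count them all as events, or count them all as non-events.

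**The concern.** The study device is used once, during the index procedure, and no study treatment continues after it. What remains for a discharged subject is mainly the day-30 and day-180 follow-up. Non-compliance after discharge is therefore largely a matter of follow-up contact. That is a reason to switch to records, and it does not make the outcome unobtainable.

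Once participation has ended on this ground, no section tells the site to go on ascertaining vital status or endpoint events, even though the subject has not withdrawn consent. The primary analysis uses observed data, so a subject terminated before a 30-day outcome is known leaves the reported rate. If poor compliance goes with being unwell, the reported composite is too low.

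The 180-day rates of death, recurrent MI, shock and heart failure face the same problem over a longer period. The SAP's sensitivity analyses for missing outcomes are specified for the 30-day primary endpoint only.

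**Working it through.** **1. The text, side by side**

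| Question | What 12.2 gives | What other sections give |
|---|---|---|
| Is termination for non-compliance optional? | The opening sentence of the bullet is discretionary; the next is mandatory | Nothing |
| Does follow-up stop? | Ruled out for withdrawn subjects, in the consent bullet; the investigator bullet is silent but ends participation | 12.3: recontact and reschedule; silent on terminated subjects |
| Could outcomes still be obtained? | Not addressed | 6.7.7 and 6.7.8: phone or outside records |
| Is contact effort required first? | Only in the lost-to-follow-up bullet | 12.3: contact to reschedule |

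The gap is in the second and third rows: a means of collection exists, but nothing applies it to a subject withdrawn by the investigator.

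**2. The plan's own figures**

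Inputs (protocol 10.2, SAP section 2): 22/360 expected events, 10% attrition, 400 enrolled. Success rule (protocol 10.8, SAP 7.1): upper 95% limit below 16%.

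- 22/360 = 6.1%, and 360/0.90 = 400. Both reproduce.
- With an exact (Clopper-Pearson) limit and n = 360, success needs at most 43 events. Power at a true rate of 6.1% exceeds 99.99%, consistent with the stated 99%. With n = 400, success needs at most 49 events and power again exceeds 99.99%. Power is not the issue.

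**3. Bias in the reported 30-day rate**

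Let k subjects be lost and r be their true event rate (assumed; the documents give none). The upper bound for k is the whole allowance, 400 × 0.10 = 40.

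True rate = (22 + 40r)/400, against a reported 22/360 = 6.1%.

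| r (assumed) | Calculation | True rate |
|---|---|---|
| 12% | (22 + 4.8)/400 | 6.7% |
| 18% | (22 + 7.2)/400 | 7.3% |
| 30% | (22 + 12)/400 | 8.5% |

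If only 10 subjects were lost this way (also assumed), with 6.1% among the other 390, the true rate would be (23.79 + 10r)/400. That is 6.2% at r = 12% and 6.7% at r = 30%.

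**4. Effect on the success rule**

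- Primary analysis at 22/360: exact upper limit 9.1%, passes.
- Most adverse row above, 34/400: exact upper limit 11.7%, still below 16%.
- SAP worst case with 40 missing: 22 + 40 = 62, and 62/400 has an exact upper limit of 19.4%, above 16%. At about 6.1% observed, the worst-case analysis first fails at 27 missing (27/400 = 6.8%): about 23 observed events plus 27 is 50, one more than the 49 allowed.

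So the primary conclusion is robust to plausible bias. The worst-case analysis becomes inconclusive within the planned attrition, and each outcome recovered from records makes it more informative.

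**The case against.** A reader might infer that 12.2 orders the study to discard safety outcomes, or that it flatly contradicts 10.4 and 12.3. The documents do not support either reading.

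- The sentence ruling out follow-up stands in the consent-withdrawal bullet, where it is proper. Extending it to investigator withdrawal is an inference from its general wording. Data already collected are not deleted.
- A patient who simply stops answering is covered by the lost-to-follow-up bullet, and one who refuses contact may fall under voluntary withdrawal. A missed day-30 contact does not by itself end participation.
- A readmission that causes a missed visit calls for an adverse event form under 12.3. Protocol 7.6.1 requires endpoint events, all SAEs and all deaths to be reported.
- Recontact and record retrieval can come before termination, so the sections can be followed in sequence. The section's lead-in and the bullet's opening are permissive.
- The SAP's worst-case analysis is harsher than the assumed 12% to 30%, and discontinuations are tabulated by reason.
- The consent wording is not available here, so permission to use records after termination cannot be confirmed.

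These points narrow the concern and leave part of it standing. The reporting duties do not say that they continue after participation is terminated. The worst-case analysis discloses missing 30-day outcomes but does not recover them. The mandatory sentence remains, with no contact effort attached to it and no provision for what follows.

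**Conclusion.** The point holds as a gap and an ambiguity in 12.2. Termination for non-compliance is permissive in one sentence and mandatory in the next. The scope of the no-follow-up sentence is unclear. No section keeps outcome collection going for subjects who have not withdrawn consent. In a single-use device study with phone and record-based visits, this loses obtainable endpoint data and sits poorly with the aims of 10.4 and 12.3.

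As an upper bound, the 30-day rate would be understated by 0.6 to 2.4 percentage points (6.1% reported against 6.7% to 8.5% true). This assumes that all 10% attrition comes from this rule and that the lost subjects' event rate is 12% to 30%. The documents give no number of such terminations, and the likely effect is smaller. A reader might infer that the primary result is at risk; it is not, because the 16% criterion is met throughout that range. The gain from a fix is less bias in the reported rates, above all at 180 days, where termination has longer to act. No figure can be given for that effect from the documents.

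**What to change.** In protocol 12.2:

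1. Confine the end of follow-up to withdrawal of consent.
2. State that subjects who do not comply, or whom the investigator withdraws, and who have not withdrawn consent, continue to have vital status and endpoint events collected through day 180 by phone or from records. This uses the route in 6.7.7 and 6.7.8 and applies as far as the consent form permits.
3. Reconcile the permissive and mandatory sentences in the investigator-withdrawal bullet. The investigator's judgement of best medical interest is left as it is.

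The cost is protocol wording, a check of the consent form, and some site time requesting records for what should be a small number of subjects. No new visit or assessment is needed.
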